Patients who achieve response status of immune-related complete response (irCR), immune-related partial response (irPR), immune-related stable disease (irSD), or unconfirmed immune-related progressive disease (irPD), per the immune-related response criteria (Appendix 6) at the end of the Cycle 1 radiographic disease assessment, may be eligible to receive subsequent administrations of MGD007 and MGA012 for up to 12 cycles (~ 2 years), assuming that the patients remain clinically stable and have not experienced DLTs that necessitated permanent discontinuation of study drug.

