For patients who are otherwise clinically stable, but have met conventional criteria for PD, therapy may be continued at the discretion of the Investigator pending confirmation of progression at the next scheduled tumor assessment. This approach allows for limited treatment of patients beyond the initial radiographic documentation of disease progression, assuming that patients are tolerating therapy adequately, that patients remain otherwise clinically stable despite this initial radiographic evidence of disease progression and that the Investigator feels the patient may still derive benefit from continuation of therapy. Treatment of patients according to irRECIST principles is supported by well-documented evidence that in some patients treated with T-cell directed, immune-modulatory agents, tumors can evolve

to an objective response after an initial period, characterized by either apparent radiographic growth of target lesions or the development of new target lesions that would otherwise meet the criteria for disease progression using conventional response criteria.

For patients in whom progression is confirmed at the next scheduled tumor assessment, the criteria for irPD will have been met, and treatment with MGD007 and MGA012 should be discontinued. The patient should be removed from study participation after completion of the Post-treatment Follow-up period (see [Section 9.12](#)). However, for individual patients who meet these criteria, but who are otherwise considered to be experiencing clinical benefit in the judgment of the Investigator, consideration may be given to continue treatment with the MGD007 and MGA012 combination, on a case-by-case basis, in consultation with the Sponsor; see [Section 5.4](#).

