**Immune-related response determination per irRECIST**

Target Lesions	Non-Target Lesions	%Change Tumor Burden	Immune-Related Response Status
CR	CR	-100%	irCR
PR	Any	≤-30%	irPR
PR	Any	≥-30% to <+20%	irSD
PR	Any	≥+20%	irPD
SD	Any	≥-30% to <+20%	irSD
SD	Any	≥+20%	irPD
PD	Any	≥+20%	irPD

No new lesions allowed to achieve irCR status. Otherwise, presence or absence of new measurable or new non-measurable lesions does not affect response status in isolation. New measurable lesions added to cumulative tumor burden to calculate % change tumor burden for the determination of immune-related response status.

**Immune-Related Complete Response (irCR):** Complete disappearance of all target and non-target lesions and no new lesions. The short axis of all lymph nodes must be ≤ 10 mm.

**Immune-Related Partial Response (irPR):** The sum of diameters has decreased ≥ 30% from the baseline but does not meet the criteria for irCR.

**Immune-Related Stable Disease (irSD):** The patient does not meet criteria for irCR, irPR or irPD.

**Immune-Related Progressive Disease (irPD):** The sum of diameters for target lesions and new measureable lesions has increased by ≥ 20% from the nadir sum of diameters.

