5 ENDPOINTS

5.1 Efficacy Endpoints

5.1.1 Response Endpoints

- Response by RECIST v1.1: The best overall response (BOR) will be categorized as CR, PR, SD, PD, or NE. To be qualified as BOR, CR and PR require confirmation at least 4 weeks after initial observation of such response, and SD requires to be observed at least once after 8 weeks (minus 3 days) from the start of MGD007 treatment.
- Immune related Response by irRECIST: The best overall response (BOR) will be categorized as irCR, irPR, irSD, irPD, or irNE. To be qualified as BOR, irCR, irPR, and irPD require confirmation at least 4 weeks after initial observation of such response, and irSD requires to be observed at least once after 8 weeks (minus 3 days) from the start of MGD007 treatment.

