5.1.2 Time to Event Endpoints

- Progression-free survival (PFS): The PFS is defined as the time from the first dose date of MGD007 to the date of first documented progression or death from any cause, whichever occurs first. For patients who are not known to be dead or progressed at the time of data cut-off for PFS analysis, the PFS will be censored at the date of the last tumor assessment. The documented progression is determined by radiographic assessment using RECIST v1.1. PFS will be calculated as:

$$\text{PFS (months)} = (\text{date of event [documented progression or death] or date of censoring} - \text{first dose date} + 1) / (365.25/12)$$

- Immune related PFS (irPFS): The irPFS is defined as the time from the first dose date of MGD007 to the date of first documented immune related progression (irPD) or death from any cause, whichever occurs first. For patients who are not known to be dead or progressed at the time of data cut-off for irPFS analysis, the irPFS will be censored at the date of the last tumor assessment. The documented irPD is determined by radiographic assessment using irRECIST. The irPFS will be calculated as:

$$\text{irPFS (months)} = (\text{date of event [documented immune related progression or death] or date of censoring} - \text{first dose date} + 1) / (365.25/12)$$

- Duration of response (DoR): The DoR is defined as the time from the date of initial response (CR or PR) to the date of first documented progression or death from any cause, whichever occurs first. The DoR is calculated only for the responders. For responders who are not known to be dead or progressed at the time of data cut-off for DoR analysis, the DoR will be censored at the date of the last tumor assessment. The documented progression is determined by radiographic assessment using RECIST v1.1. DoR will be calculated as:

$$\text{DoR (months)} = (\text{date of event [documented progression or death] or date of censoring} - \text{date of initial response} + 1) / (365.25/12)$$

DoR may also be determined by irRECIST.

- Overall survival (OS): The OS is defined as the time from the first dose date of MGD007 to the date of death from any cause. For patients who are not known to be dead at the time of data cut-off for OS analysis, the OS will be censored at the time they are last known to be alive. OS will be calculated as:

$$\text{OS (months)} = (\text{date of death or last known alive} - \text{first dose date} + 1) / (365.25/12)$$

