6.6.2 Analyses of Time to Event Endpoints

6.6.2.1 PFS and irPFS

The Kaplan-Meier method will be applied to estimate PFS curve, median PFS, and PFS rates at 4 (corresponding to 16 weeks), 6, and 12 months. The method of Brookmeyer and Crowley (1) will be used to construct 95% CI for median PFS. The 95% CIs for PFS rate at 4, 6, and 12 months will be calculated by normal approximation after log(-log) transformation.

For primary PFS analysis, the following table describes the censoring rules.

Table 2 Censoring Rules for Primary PFS Analysis

Situation	Date	Outcome
No baseline tumor assessments	First dose date	Censored
Death prior to first scheduled tumor assessment	Date of death	Progressed
No post-baseline tumor assessments in absence of death prior to first scheduled tumor assessment	First dose date	Censored
Documented progression	Date of progression	Progressed
Initiation of alternative anti-cancer treatments in absence of documented progression	Date of last tumor assessment prior to initiation of such treatment	Censored
Death or documented progression immediately after missing two or more consecutive scheduled tumor assessments	Date of last tumor assessment prior to missed assessments	Censored

PFS will be analyzed by MMR status and by KRAS gene type when sample size warrants. A sensitivity analyses for PFS may be performed to assess the robustness of above primary PFS analysis. For this sensitivity analysis, the censoring rules are the same as in **Table 2** except that the documented progression or death will be considered as an event, regardless of when it occurs during the study.

In addition, above analyses for PFS will also be repeated for irPFS.

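### irPFS: the SAP defines neither the scan that dates the event nor how a never-confirmed irPD is counted, and the readings the documents allow give very different 16-week rates

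*SAP*

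**What the plan says.** SAP 5.1.2 ends irPFS at "first documented immune related progression (irPD) or death from any cause". For patients not known to have died or progressed, "the irPFS will be censored at the date of the last tumor assessment". SAP 6.6.2.1 repeats the PFS analyses for irPFS, including the Table 2 row "Initiation of alternative anti-cancer treatments in absence of documented progression", which censors at the last scan before the new therapy. The 16-week rate under irRECIST is part of the primary expansion objective (Protocol 3.2.1, SAP 2.2.1).

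On whether irPD needs confirmation, the documents point both ways.

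- **Towards confirmation.** Protocol 11.1.1, echoed in the Synopsis: "For patients in whom progression is confirmed at the next scheduled tumor assessment, the criteria for irPD will have been met". SAP 5.1.1, for best overall response: "irCR, irPR, and irPD require confirmation at least 4 weeks after initial observation of such response".
- **Towards a single scan.** The Synopsis and Protocol 4.1 list, among the statuses that permit further cycles, "or unconfirmed immune-related progressive disease (irPD"). The response table in Appendix 6 defines irPD from one time point: "The sum of diameters for target lesions and new measureable lesions has increased by" at least 20% over the nadir. Appendix 6 section 2.4.1 describes patients who already have irPD and then need a scan 4 or more weeks later to confirm it.

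Appendix 5 (sections 2.2.5 and 2.3.3) dates an equivocal RECIST progression, once confirmed, back to the earlier scan. Appendix 6 has no matching sentence.

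**The concern.** A programmer who follows Protocol 11.1.1 and SAP 5.1.1 would treat irPD as documented only at the confirming scan. Two things then happen to irPFS. Confirmed progressors are dated one scan late. Patients who stop at a first irPD and are not rescanned, or who start new therapy, have no event and are censored at their last scan. That censoring is informative, because a patient at a first irPD is not at average risk.

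The schedule makes missing confirmation likely. The last Cycle 1 MGD007 dose is Day 50 and the scan is Day 56. The End of Treatment Visit is due within 30 days of the last dose, so by about Day 80, which is 24 days after the scan. Protocol 9.11 waives the visit scan if one was done less than 28 days before, and treats the visit as optional. A scan at that visit would also fall short of the 4-week minimum.

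A programmer who follows Appendix 6 would date the event at the first irPD scan. That removes the inflation, but an irPD that later reverses still counts as progression. This runs against the rationale in Protocol 11.1.1 that apparent growth can precede response. A primary measure would then depend on a choice left to programming.

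**Working it through.** **The plan's own figure.** The documents give no planned irPFS rate, null value or power. The only sample-size figures are the exact binomial intervals in SAP Table 1 (Protocol Table 13). All six rows reproduce to one decimal; for example, 6 of 25 gives 9.4% to 45.1%.

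**Inputs**
- n = 25 (Protocol 14.1). Scans at Day 56, then every 8 weeks: 112, 168 (Protocol 11.1.1).
- Landmark: SAP 6.6.2.1 uses 4 months. By the SAP 5.1.2 formula this is 4 × 365.25/12 = 121.75 days; 16 weeks is 112 days. The results below are at 121.75 days.
- Progression speed (assumption): Protocol 2.2 gives median PFS of 1.7 to 2.0 months in later-line trials. Under an exponential curve, S(t) = 2^(−t/median), so 47% to 53% are free at Week 8 and 22% to 28% at Week 16. In 25 patients this is roughly 13 first irPDs at Week 8, 6 at Week 16 and 6 free.
- The share of irPDs confirmed, and deaths before a rescan, are not given in the documents and are varied.

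**Kaplan-Meier results, base pattern 13/6/6**

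1. Event at the first irPD scan, all counted: (12/25) × (6/12) = 24.0% (95% CI 9.8 to 41.7, log(−log)).
2. Dated at the confirming scan, all confirmed: the 13 Week 8 progressors become events at Day 112 with 25 at risk, and the 6 Week 16 progressors move to Day 168. 12/25 = 48.0% (27.8 to 65.6).
3. As 2, with about half confirmed (6 of 13 and 3 of 6): 7 are censored at Day 56, leaving 18 at risk at Day 112 with 6 events. 12/18 = 66.7% (40.4 to 83.4).
4. As 2, with about 75% or 25% confirmed: 12/22 = 54.5% or 12/15 = 80.0%.
5. Confirmed irPD dated back to the first scan but unconfirmed irPD censored, about half confirmed: (19/25) × (9/12) = 57.0%. Back-dating alone does not remove the problem.

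A confirming scan at 4 weeks instead of 8 leaves results 2 to 4 unchanged. In result 2 the Week 8 progressors are still events by the landmark; the rise from 24% to 48% comes from the Week 16 progressors moving past it.

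**Other assumed patterns** (Week 8 / Week 16 / free)

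| Pattern | First scan | Confirming scan, all confirmed | Confirming scan, about half |
|---|---|---|---|
| 8/4/13 | 52.0% | 68.0% | 81.0% |
| 13/6/6 | 24.0% | 48.0% | 66.7% |
| 13/9/3 | 12.0% | 48.0% | 66.7% |

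**Deaths.** Take 7 of the 13 Week 8 irPDs as confirmed and 6 as not. If 0, 2, 4 or 6 of those 6 die before Week 16, the rate is 12/19 = 63.2%, 12/21 = 57.1%, 12/23 = 52.2% or 12/25 = 48.0%.

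**Reversal.** Suppose 2 of the 13 Week 8 irPDs reverse and stay free (assumption). First-scan dating still gives 6/25 = 24%. A rule that cancels reversed irPD gives 8/25 = 32%.

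**The case against.** The strongest reply is that the SAP already says enough. Documented irPD is determined radiographically by irRECIST, irRECIST in Appendix 6 assigns irPD from one scan, and irPFS takes the first such date. On that reading nothing is dated late, and the Table 2 new-therapy row does not apply because progression is already documented. The confirmation sentences have other jobs: SAP 5.1.1 governs best overall response, and Protocol 11.1.1 concerns stopping treatment. This stands as a reasonable reading, but no section selects it, and it leaves reversed irPD as an event.

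A reader might infer more: that irPD exists only once confirmed, so the irPFS rate must be inflated. The Synopsis, Protocol 4.1 and Appendix 6 all use irPD before confirmation, so the documents do not support that.

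A reader might also infer that Week 8 progressors escape by being dated at Week 16, with rates near 100%. If all 13 confirming scans fell on Day 115, the rate would be 100% at Day 112 but 48% at 121.75 days. Similarly, take the monotherapy study's 30 of 59 (51%) with progressive disease as a Week 8 irPD rate, with half never confirmed and half of the confirming scans after Day 112. Per 100 patients this gives 1 − 12.75/74.5 = 83% at Day 112, but 1 − 25.5/74.5 = 66% at 4 months. That 51% is also a RECIST best response, and new lesions alone are not irPD, so it is a poor proxy.

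Other mitigations are partial:
- Deaths count as events and shrink the censoring effect.
- Protocol 11.1.1 has physicians contacted every 3 months about patients who stopped without confirmed progression. Protocol 9.12 limits response follow-up to those who stopped for reasons other than progression and have started no new therapy.
- The RECIST 1.1 rate is reported alongside, but the two criteria differ anyway in how they treat new lesions, so a gap would not reveal its cause.
- The sensitivity analysis in SAP 6.6.2.1 changes when an event counts, not what irPD is or when it is dated.
- The separate programming plan may settle the matter, but it is not among the documents, and an endpoint definition belongs in the SAP.

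**Conclusion.** The point holds as a gap in definition with a material consequence. The documents conflict on whether irPD needs confirmation, and no section dates the irPFS event or says how a never-confirmed irPD is handled. In the base pattern the allowed readings give 24%, 48% or about 67% for the same patients.

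These sizes rest on an assumed progression pattern taken from other treatments' median PFS, an assumed share confirmed, no deaths before rescan unless stated, and the 4-month landmark. They show how far the result can depend on the reading; they do not forecast this trial. If the first scan is meant, there is no inflation, and the remaining fault is that reversed irPD counts as progression. The analyses are descriptive, so no test is affected. The estimate is still a primary one and should be settled before data are seen.

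**What to change.** In SAP 5.1.2 and 6.6.2.1, and for DoR by irRECIST in 6.6.2.2:

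- Date the irPFS event at the first irPD scan, unless a later scan at least 4 weeks afterwards shows irSD, irPR or irCR.
- Count a first irPD followed by no further scan, new therapy, clinical progression or death as an event on the date of that first irPD.
- Report, as a sensitivity analysis, the version in which unconfirmed irPD is censored.

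This also settles the Table 2 new-therapy row, because a first irPD that has not reversed is then documented progression. The cost is SAP text and programming, with no new data. The irPFS rate may be less favourable than under the confirmed-irPD reading.

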5.2 Safety Endpoints

5.2.1 Adverse Events

Adverse event (AE) means any untoward medical occurrence in a patient or clinical trial patient associated with the use of a drug in humans, whether or not considered drug related. An adverse event can therefore be any unfavorable and unintended sign (including an abnormal laboratory finding, for example), symptom, or disease temporally associated with the use of a medicinal product, whether or not considered related to the medicinal product.

AEs will be captured starting from date of first study drug through end of treatment visit or 30 days following last dose of study drug (whichever is later). Only treatment-related serious AEs will be captured afterwards. These events will be recorded by the Investigators in the eCRFs. Verbatim terms will be coded to lower-level terms using the most recent version of the Medical Dictionary for Regulatory Activities (MedDRA). An assessment of severity grade will be made using National Cancer Institute-Common Terminology Criteria for Adverse Events (NCI-CTCAE) Version 4.03.

AEs reported between the time the patient signs the informed consent form and the administration of the first dose of study drug will be captured as medical history unless the AE is attributable to protocol-specified procedures that are not part of standard of care that occur during this time period, in which case the AE will be collected as AEs on the Adverse Event CRFs. Only treatment emergent adverse events (TEAEs) will be summarized in tables. A TEAE is defined as any event that is newly occurring on or after the administration of

study drug or an event that existed before but increased in severity on or after study drug administration.

5.2.2 Laboratory Evaluations

Standard safety laboratory parameters collected via a local laboratory will be summarized and graded according to CTCAE Version 4.03. A laboratory abnormality should be reported as an AE if it is associated with an intervention. An intervention includes, but is not limited to, discontinuation of treatment, dose reduction/delay, or concomitant therapy. In addition, any medical important laboratory abnormality may be reported as an AE at the discretion of the investigator.

5.2.3 Vital Signs and ECOG Performance Status

Vital signs include temperature, pulse, blood pressure, and respiratory rate. Vital signs and ECOG performance status will be performed according to the schedules outlined in the latest version of the protocol.

5.2.4 Electrocardiograms

All ECGs should be obtained in triplicate (3 ECGs per time point at approximately 1-minute intervals) according to the schedules outlined in the latest version of the protocol in order to evaluate the potential cardiac effects of study drug, including QT interval prolongation.

5.3 Pharmacokinetic, Pharmacodynamic, and Immunological Parameter Endpoints

PK samples, anti-drug antibody (ADA) samples and pharmacodynamic biomarker specimens will be collected according to the schedules outlined in the latest version of the protocol.

5.4 KRAS Mutation and MMR Status

Data regarding the KRAS and MMR mutational status (microsatellite instability [MSI-H] or microsatellite-stable [MSS]) will be collected for all patients; statuses for both must be formally documented for patients in the Cohort Expansion Phase.

6 STATISTICAL METHODOLOGY

6.1 General Considerations

This study is primarily observational and, thus, the majority of the statistical summaries will be descriptive. Safety and efficacy summaries will be provided for each dose level cohort during dose escalation and for all dose level cohorts combined, as well as for expansion cohorts where appropriate. Response rates will be calculated for the response evaluable population.

Unless otherwise specified, the following general considerations are applied in data analyses:

- The baseline value is defined as the latest value prior to the first dose of MGD007 treatment.
- Categorical data will be summarized by the number and percent of patients falling within each category.
- Continuous variables will be summarized by descriptive statistics, including mean, standard deviation, median, minimum, and maximum.
- Time-to-event endpoints will be summarized by the number and percent of the event, median time and corresponding 95% confidence interval (CI), and event free rate and corresponding 95% CI at the specified time points of interest.
- All data summaries and tabulations will be conducted using SAS® software Version 9.3 or higher.

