## 4 STUDY DESIGN

### 4.1 Overall Study Design and Plan

[figure not shown]
This study is an open-label, Phase 1b/2 dose escalation and cohort expansion study designed to characterize the safety, tolerability, PK, pharmacodynamics, immunogenicity, and preliminary antitumor activity of MGD007 and MGA012, administered in combination by IV infusion, in patients with histologically proven, relapsed/refractory metastatic colorectal carcinoma, irrespective of the KRAS and MMR status of their tumors. This study will enroll patients as described below.

The study will proceed in 2 distinct phases as follows: Dose Escalation Phase to determine the MTD or MAD (if no MTD is defined) of the combination, followed by a Cohort Expansion Phase to further define the safety and initial antitumor activity of the combination with the doses established in the Dose Escalation Phase.

Patients will be treated with MGD007 and MGA012 as shown in [Figure 11](#). MGD007 will be administered at the target dose for each assigned cohort as an IV infusion over 120 minutes, once weekly (QW), in 8-week treatment cycles. MGA012 will be administered at 3 mg/kg as an IV infusion over 60 minutes, once every 2 weeks (Q2W) beginning on Cycle 1 Day 15, and every 2 weeks thereafter. For each patient, administration of the first dose of MGA012 will occur 2 weeks after the first dosing of MGD007. The DLT evaluation period will last until Cycle 1 Day 42. Disease status will be evaluated on Cycle 1 Day 56 ( $\pm$  3 days) using CT and/or MRI as appropriate for the sites of disease, accompanied by physical examination, and will then be evaluated every 8 weeks while on study treatment. Although response assessment will be performed according to both conventional (RECIST 1.1 [\[Appendix 5\]](#)) and irRECIST ([Appendix 6](#)), patients will be managed according to irRECIST principles. This approach allows for limited treatment of patients beyond the initial radiographic documentation of disease progression, assuming that the Investigator feels that the patients are tolerating therapy adequately, that patients remain otherwise clinically stable despite this initial radiographic evidence of disease progression, and that the Investigator feels the patient may still derive benefit from continuation of therapy.

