### **Appendix 3      Pharmacokinetics, Immunogenicity, and Pharmacodynamic Biomarkers Blood Sampling Schedule for MGD007 & MGA012**

Blood samples for MGD007 and MGA012 PK, ADA, and PD biomarkers will be collected per [Table 15](#).

**Table 15 Pharmacokinetic, Immunogenicity, and Pharmacodynamic Biomarkers Blood Sampling Schedule for MGD007 & MGA012 **

Cycle	Day	MGD007 & MGA012 PK Sampling Time 	MGD007 & MGA012 ADA Sampling Time	Cytokines 	Flow Cytometry Occupancy	Flow Cytometry Subsets	Serum Bio-markers 	T-cell repertoire 	ctDNA analysis 	Transcript profile 
1	1	Pre MGD007 infusion	Pre MGD007 infusion	Pre MGD007 infusion	Pre MGD007 infusion	Pre MGD007 infusion	Pre MGD007 infusion	Pre MGD007 infusion	Pre MGD007 infusion	Pre MGD007 infusion
	1	End of MGD007 infusion								
	1	2 hours after end of MGD007 infusion		2 hours after end of MGD007 infusion	2 hours after end of MGD007 infusion	2 hours after end of MGD007 infusion				
	1	6 hours after end of MGD007 infusion		6 hours after end of MGD007 infusion						
1	2			Day 2	Day 2	Day 2				
1	8	Pre MGD007 infusion			Pre MGD007 infusion	Pre MGD007 infusion	Pre MGD007 infusion			
	8	End of MGD007 infusion								
	8				2 hours after end of MGD007 infusion	2 hours after end of MGD007 infusion				
1	15	Pre MGA012 infusion	Pre MGA012 infusion	Pre MGA012 infusion	Pre MGA012 infusion	Pre MGA012 infusion	Pre MGA012 infusion			

**Table 15 Pharmacokinetic, Immunogenicity, and Pharmacodynamic Biomarkers Blood Sampling Schedule for MGD007 & MGA012 **

Cycle	Day	MGD007 & MGA012 PK Sampling Time 	MGD007 & MGA012 ADA Sampling Time	Cytokines 	Flow Cytometry Occupancy	Flow Cytometry Subsets	Serum Bio-markers 	T-cell repertoire 	ctDNA analysis 	Transcript profile 
1	15	End of MGA012 infusion								
	15	End of MGD007 infusion								
	15				2 hours after end of MGD007 infusion	2 hours after end of MGD007 infusion				
	15	1 hour after end of MGD007 infusion								
	15	2 hours after end of MGD007 infusion								
	15	4 hours after end of MGD007 infusion								
	15			6 hours after end of MGD007 infusion						
1	16	Day 16		Day 16	Day 16	Day 16				
1	17	Day 17								
1	19	Day 19								

**Table 15 Pharmacokinetic, Immunogenicity, and Pharmacodynamic Biomarkers Blood Sampling Schedule for MGD007 & MGA012 **

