4 ANALYSIS POPULATIONS

4.1 Analysis Populations

The study analyses will be performed on the following populations:

- **Safety Population:** All patients who received at least one dose of any study drug. This population will be used for analyses of safety, PD, and immunogenicity. It will also be used for summary of baseline data and analyses of PFS and OS.
- **Response Evaluable Population:** All patients who received at least one dose of any study drug, had baseline measurable disease, and had at least one post-baseline radiographic tumor assessment or discontinued treatment due to clearly documented, clinically progressive disease or death. This population will be used for summary of tumor assessment data and analyses of response rates.

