6.8 Pharmacokinetic, Pharmacodynamic, and Immunological Parameter Endpoint Analyses

Pharmacokinetic Analysis: Summary statistics will be tabulated separately for serum PK parameters by MGD007 and MGA012 dose. Geometric means and percent coefficients of variation will be reported for C_{\max} , $AUC_{(0-T)}$, $AUC_{(TAU)}$, $AUC_{(INF)}$, and C_{trough} ; arithmetic means and standard deviations will be reported for $t_{1/2}$, CL, and V_{ss} ; and medians, minimum, and maximum will be reported for T_{\max} . Separate scatter plots of C_{\max} and AUC will be

provided versus dose to assess dose dependency. Dose proportionality may be assessed using a power model. Population PK analyses may be conducted using data from this study alone or combined with data from other studies.

Immunogenicity Analysis: The proportion of patients who are negative for ADA at baseline and become positive in this assay, the proportion of patients who are negative at baseline and remain negative, and those who have positive ADA at baseline that increases or decreases in titer over the course of treatment will be summarized. Analysis will be conducted separately for MGD007 and MGA012.

Pharmacodynamic Analysis: Summary statistics for pharmacodynamic parameters and corresponding changes from baseline will be summarized and/or may also be presented graphically as well as possible associations between changes in pharmacodynamic measures of interest and MGD007 in combination with MGA012 dose and exposure may be explored.

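### The MGA012 ADA analysis uses a baseline set before MGD007 and a population that needs no MGA012 dose, so a positive drawn before first exposure counts as conversion

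*SAP*

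**What the plan says.** **Baseline.** SAP 6.1 lists rules introduced by "Unless otherwise specified, the following general considerations are applied in data analyses". One of them is "The baseline value is defined as the latest value prior to the first dose of MGD007 treatment". It makes no distinction between the two drugs.

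**Population.** SAP 4.1 defines the Safety Population as "All patients who received at least one dose of any study drug" and adds "This population will be used for analyses of safety, PD, and immunogenicity". Protocol 14.2 agrees. Neither document defines a set of ADA-evaluable or MGA012-exposed patients.

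**ADA summary.** SAP 6.8 reports "The proportion of patients who are negative for ADA at baseline and become positive in this assay", then those who start and stay negative, then titer changes in those positive at baseline. It adds "Analysis will be conducted separately for MGD007 and MGA012". It gives no other baseline and no explicit denominator. Protocol 14.5.2 is worded the same way.

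**Timing.** Protocol 4.1 states that "administration of the first dose of MGA012 will occur 2 weeks after the first dosing of MGD007", that is, on Cycle 1 Day 15 (C1D15). In Table 15 (Protocol Appendix 3), the ADA column has a sample on C1D1 before MGD007 and another on C1D15 marked "Pre MGA012 infusion". It also has later samples and one at the end-of-treatment (EOT) visit.

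**The concern.** A per-drug ADA conversion rate should count patients who turn positive after exposure to that drug, among patients who were exposed to it. For MGD007 the single baseline and the Safety Population both fit. For MGA012 neither does.

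The C1D15 pre-infusion sample is drawn with no MGA012 yet given, but under SAP 6.1 it falls after baseline. A positive there, following a negative on Day 1, meets the SAP's definition of becoming positive. The population rule also admits patients who received only MGD007.

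What is at stake is the meaning of the reported MGA012 ADA incidence, which serves the immunogenicity part of a secondary objective in both phases. Pre-exposure positives raise the rate and unexposed negatives lower it. A reader of the final table could not tell how much of either it contains.

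**Working it through.** The plan gives no ADA rate, ADA sample size or ADA precision, so there is no figure to reproduce. The check follows the rules through and then illustrates their effect.

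**Step 1: place the samples.** First MGD007 is Day 1 and first MGA012 is Day 15, a gap of 15 − 1 = 14 days. Two scheduled ADA samples precede any MGA012: C1D1 and C1D15 pre-infusion. SAP 6.1 selects C1D1 as baseline, so one scheduled sample is post-baseline but pre-exposure.

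**Step 2: classify a patient negative on C1D1 and positive on C1D15 pre-infusion.** Under SAP 6.8 this patient becomes positive for MGA012. With the last sample before MGA012 as baseline, the same patient is positive at baseline and belongs in the titer-change category.

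**Step 3: classify a patient who stops before Day 15.** One dose of MGD007 puts the patient in the Safety Population. The only scheduled ADA sample after Day 1 is at EOT. If it is taken, the patient can be classed as remaining negative or becoming positive for MGA012 without receiving it.

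**Step 4: size of one pre-exposure positive.** N = 25 is the planned expansion size, and 27 + 25 = 52 is the total in Protocol 14.1. SAP 3.2 still shows 104 because it retains the removed Q2W cohort; the protocol figure is used here.

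- N = 25: 1/25 = 4.0 percentage points.
- N = 52: 1/52 = 1.9 percentage points.

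The chance of at least one such patient is 1 − (1 − f)^N, where f is the proportion turning positive between C1D1 and C1D15 pre-infusion. The documents give no f; 1% to 5% is an assumed range.

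| f (assumed) | N = 25 | N = 52 |
|---|---|---|
| 1% | 22% | 41% |
| 2% | 40% | 65% |
| 5% | 72% | 93% |

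**Step 5: size of the denominator effect.** Assume 3 true converters, all MGA012-treated, and d patients who never receive MGA012 but are classified as remaining negative. The SAP rate is 3/N and the exposed-patient rate is 3/(N − d).

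| d (assumed) | SAP, N = 25 | Exposed only |
|---|---|---|
| 1 | 3/25 = 12.0% | 3/24 = 12.5% |
| 2 | 12.0% | 3/23 = 13.0% |
| 3 | 12.0% | 3/22 = 13.6% |
| 5 | 12.0% | 3/20 = 15.0% |

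At N = 52 the SAP rate is 3/52 = 5.8%, against 3/51 = 5.9% to 3/47 = 6.4% for d = 1 to 5. For scale, the exact 95% interval for 3/25 is 2.5% to 31.2% (SAP Table 1).

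**Step 6: an unexposed patient need not dilute.** Take 24 exposed patients with 3 converters (12.5%) and one early stopper who is negative on Day 1 and positive at EOT. The SAP rate becomes 4/25 = 16.0%.

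**The case against.** **The numbers are small, assumed and offsetting.** Neither the pre-exposure positive rate nor the number stopping before Day 15 is given. The shifts in Step 5 are small beside an interval of 2.5% to 31.2%, and the two effects can offset. SAP 6.1 describes the study as mainly observational, with mostly descriptive summaries. All of this stands and limits the weight of the point. It does not make the rule right, because offsetting by chance is not control.

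**The denominator is not settled.** SAP 6.8 states none, Protocol 9.11 makes the EOT visit optional, and SAP 6.2 leaves missing data missing. An early stopper without an EOT sample can be called neither converted nor persistently negative. The separate statistical programming plan, which is not among the documents, could also restrict the set. This stands in part: one cannot infer that every early stopper enters the MGA012 denominator. But the population named in the SAP admits those who do have a sample. Protocol 5.4 foresees dose-limiting toxicity before MGA012 starts, so such patients are possible, although it allows some to continue on MGA012 alone.

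**Stronger readings that the documents do not support:**

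- *That a baseline before any MGA012 is itself wrong.* Every ADA baseline must precede the drug. The fault is using Day 1 when a later pre-exposure sample is scheduled.
- *That unexposed patients can only add to the persistently negative group.* Step 6 shows otherwise.
- *That the pharmacodynamic analysis has the same defect.* Only the immunogenicity paragraph of SAP 6.8 calls for analysis by drug. The pharmacodynamic objective concerns the combination, for which a Day 1 baseline is legitimate. With that baseline, the change at C1D15 pre-infusion already shows MGD007 alone. Change from C1D15 onward would not isolate MGA012, because MGD007 continues weekly and there is no control arm. The documents do not say that the two-week lead-in was meant to separate the drugs.

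**Conclusion.** The point holds for MGA012 immunogenicity only. Applying SAP 6.1, 4.1 and 6.8 together, a positive drawn before the first MGA012 dose is counted as conversion to MGA012, and a patient never given MGA012 can be classified for it if an EOT sample exists. The first follows directly from the written rules. The second depends on someone stopping before Day 15 and attending an optional visit.

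Each pre-exposure positive adds 4.0 points at N=25 or 1.9 at N=52. With 3 assumed converters, 1 to 5 never-exposed patients among 25 account for a difference between 12.0% and 12.5% to 15.0%. How often either event occurs is unknown. No efficacy result, sample size or error rate is affected. The SAP should be corrected before analysis, but this is not a threat to the trial's main conclusions.

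**What to change.** 1. **SAP 6.1 and 6.8:** define the ADA baseline by drug. Keep the last sample before the first MGD007 dose for MGD007. For MGA012, use the last sample before the first MGA012 dose, normally C1D15 pre-infusion, or C1D1 if that is missing.
2. **SAP 4.1:** restrict the MGA012 ADA analysis to patients with at least one MGA012 dose, a baseline ADA sample as above, and at least one ADA sample after that dose. State this as the denominator in SAP 6.8.
3. **Pharmacodynamics:** leave the Day 1 baseline as it is. Change from C1D15 pre-infusion may be added as a supplementary summary, labelled as not isolating MGA012.

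The cost is SAP wording and matching table specifications. Table 15 already schedules every sample needed, and the SAP needs revision anyway to remove the Q2W cohort.
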